7.2.4 Diagnostic evaluation of symptoms or findings suggestive of lung disease

All diagnostic evaluations will be performed in the Clinical Centers and will follow the algorithms devised for purposes of the protocol (Section 7.2.7). The diagnostic evaluation may be triggered by the occurrence of symptoms (noted either at the time of a scheduled evaluation or between evaluations) or by chest radiograph detected on scheduled screening examinations. Standard methods to be used for each of the studies are described in Appendix 5. All data will be recorded on standard forms.

The symptoms that will trigger an evaluation include:

Table 6
Schedule of Interval Laboratory Studies

Frequency of studies (months)
(See text for definitions of group)

Study	Group A-1(1)	Group A-2	Group B-1(1)	Group B-2	Group C(1)	1-month F/U (all groups)(2)
History Performance status	6	3	6	3	6	+
Physical Exam	6	3	6	3	6	+
CBC/Diff, platelets	6	3	6	3	6	+
ESR/SMA	6	3	6	3	6	+
Absolute CD-4 CD-8, CD-3(4)	6	3	6	3	6	+
Serum Bank	6	3	6	3	6	+
HIV Ab(3)	Entry	Entry	Entry	Entry	6	0
Induced Sputum	Entry	Entry	Entry	Entry		
Skin tests	12	12	12	12	12	0
PFT	12	3	12	3	12	+
CXR (PA/Lat)	12	3	12	3	12	+

(1) Subjects enrolled in Group A-1 or B-1 who later develop an HIV-related pulmonary complication will continue the same schedule, except PFT's will be performed every 6 months. The schedule of evaluations for Group C subjects who seroconvert will not change.

(2) "+" = test performed.

(3) Omit if documented positive prior to study entry.

(4) May be omitted if performed within the three months prior to visit.

1) unexplained cough that persists for more than five days;
2) unexplained breathlessness (progressive over ≥ 5 days or severe ≥ 1 day); or 3) unexplained new onset of documented fever ($\geq 38^{\circ}\text{C}$ oral ≥ 5 days). As a part of the orientation and at each routine clinic visit, each study subject will be alerted to these symptoms and instructed to contact the study office should they develop. For each of these symptoms, if a reason other than a possible HIV-related pulmonary process can be found (e.g., asthma), the evaluation will not proceed. If the subject has fever with localizing extrapulmonary symptoms (e.g., diarrhea) and no pulmonary symptoms, the evaluation will not proceed, and the subject will be referred to the primary physician. Any diagnoses resulting from such an episode will be entered at the subsequent visit on the Interval Visit Questionnaire.

Symptom Evaluation: When symptoms are reported the subject will be scheduled for a Symptom Evaluation Visit. These evaluations may be performed either on an inpatient or outpatient basis depending on the severity of symptoms and logistics of the evaluation.

The symptom evaluation visit will include:

1. Interval Visit Questionnaire.
2. Physical examination. The physical examination will be the same as that performed for the routine visits. The methods for procedures 3 through 7 are described in Appendix 5.
3. Chest radiograph (frontal and lateral views). If a radiographic abnormality is found, further evaluation will proceed as outlined in Section 7.2.7. Patients with cough and/or shortness of breath and no radiographic findings will have pulmonary function tests performed. Patients with fever but no specific pulmonary symptoms and normal chest films will be referred to their primary physicians and scheduled for a one month follow-up visit.

Based on the results of the history, physical examination, and chest radiograph, the physician investigator may make the clinical decision that the subject has acute bronchitis and elect to empirically treat the patient with antibiotics or simply observe him/her without proceeding to the items listed below. Otherwise, the following sequence of studies will be done:

4. Pulmonary function tests (lung volumes, expiratory flows and the single breath diffusing capacity for carbon monoxide (DLCO)).
Abnormalities in pulmonary function such as airways obstruction, or bronchitis, may account for the patient's symptoms. The subject will be scheduled for a one month follow-up visit.
If in a symptomatic patient other abnormalities are not detected, the next step will be lung imaging using ⁶⁷Gallium citrate.
5. ⁶⁷Gallium citrate imaging
Lung imaging using ⁶⁷Ga citrate will be performed in symptomatic subjects with normal chest radiographs and in whom other pulmonary function abnormalities do not account for the symptoms. Subjects having pulmonary parenchymal uptake of the isotope will be evaluated with sputum induction. If there is no pulmonary ⁶⁷Ga uptake, the diagnostic evaluation will not proceed further, and the subject will be scheduled for a one month follow-up visit.
6. Sputum induction All patients who have symptoms and an abnormality on chest film (as specified in Section 7.2.7), or ⁶⁷Ga scan will have sputum induced.
7. Bronchoscopic procedures
All patients who have sputum induced and who do not have a pathogen identified will undergo bronchoscopy. Bronchoscopy will be performed within two weeks of the symptom evaluation visit.
8. Blood studies
All subjects who require additional evaluation because of chest radiographic abnormality, or abnormal GA scans will have the following blood tests:
 - T-cell subset determination (if not done within 3 months)
 - Complete blood count and differential, ESR SMAC (with LDH)
 - Serum to be frozen at -70°Chest Radiograph Abnormalities: Chest radiographic abnormalities may be discovered during symptom evaluation visits or scheduled clinic visits in subjects with or without associated symptoms.

Radiographic abnormalities will be categorized as follows:

1. diffuse process (including diffuse infiltration of any pattern, multiple ill-defined densities, multiple nodules or masses)
2. focal interstitial pattern
3. focal consolidation;
4. pleural effusion;
5. intrathoracic adenopathy;
6. focal cavity lesions;
7. solitary masses or nodules;

If a chest radiographic abnormality is noted, comparison with any available previous chest radiographs will be made. If the abnormality can be documented on radiographs performed ≥ 6 months previously, and is currently unchanged or has been evaluated previously and is unchanged, the evaluation will not proceed unless there are new symptoms.

If an abnormality is found on the film of an asymptomatic subject who has no old films the evaluation may proceed directly or a second film may be obtained one month later and if there is no change the evaluation need not proceed.

The specific evaluations to be performed will depend on the kind of abnormality noted and on the clinical circumstances. The diagnostic approaches to be used for the most common kinds of abnormalities are shown in Section 7.2.7.

Pulmonary Function Abnormalities: Pulmonary function abnormalities may be identified during scheduled or symptom evaluation visits in symptomatic and asymptomatic subjects with or without chest radiograph abnormalities.

1. Subjects with chest radiographic abnormalities will be evaluated as outlined in Section 7.2.7.
2. When a subject develops an AIDS defining or AIDS associated pulmonary diagnosis (e.g., PCP, bacterial pneumonia, etc.), the subject will have a one month follow-up DLCO which will constitute the new baseline DLCO. Further, if a 20% drop in the DLCO generated an invasive diagnostic work-up that resulted in no definitive

diagnosis to explain the reduced DLCO, then the new (lower) DLCO will constitute a new baseline for that subject.

Asymptomatic subjects with abnormal spirometry will not require further diagnostic evaluation because airways obstruction have not been features of AIDS-related lung disease. The subject and the primary physician will be notified so that treatment (e.g., bronchodilators) can be started if appropriate. Any treatment that has been started will be recorded on the subsequent Interval Visit Questionnaire.

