there may be pulmonary involvement, either primary or secondary, at any point in the course of HIV disease. Although much is known about the pulmonary disorders associated with AIDS, there are very important deficiencies in the available information. These deficiencies are due in large part to clinicians and investigators focusing on those disorders that serve to define AIDS or that occur in patients who have AIDS. There is little or no information that systematically identifies the pulmonary disorders that occur at all stages of HIV disease or that describes the course patients follow after the diagnosis of a lung disease has been established.

2. Primary and Secondary Objectives

The primary objective of this study is to determine the prevalence, incidence, and types of lung diseases that occur in persons in selected HIV transmission categories with and without HIV infection and to describe the course and outcome of these disorders.

Within the context of the primary objective there are several secondary objectives that this study seeks to achieve. These are subsidiary to the primary objective but have importance in their own right.

The secondary objectives are as follows:

1. To identify demographic, clinical, and immunologic and other laboratory variables that are associated with the subsequent diagnosis of specific HIV-related lung diseases;
2. To describe the clinical, radiographic, and pulmonary physiologic, immunologic, and other laboratory variables that are associated with specific HIV-related lung diseases at the time the disease is diagnosed;
3. To determine if there is a difference in the prevalence/incidence of identified pulmonary disease, respiratory symptoms, chest radiographic abnormalities, and rates of decline in pulmonary function in subjects with HIV infection compared with these same variables in subjects from the same HIV transmission categories who do not have HIV infection;

4. To measure the frequency with which HIV-related lung diseases are present in HIV-infected persons who do not have symptoms;
5. To compare survival, days in hospital and functional status in subjects who have had lung diseases diagnosed as a result of intensive screening or evaluation of respiratory symptoms with subjects who have had the same diseases diagnosed as a result of routine screening tests or evaluation of respiratory symptoms.

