Also unexplained is the finding by Gullion and coworkers (62) of a lymphocytic alveolitis (defined as > 15% lymphocytes on BAL) in 27 (59%) of 46 HIV-infected subjects who had no respiratory symptoms, normal chest films and no lung infections or neoplasia. The mean percentage of lymphocytes was greater in symptomatic patients and in patients with radiographic abnormalities. Respiratory symptoms were consistently present when the proportion of lymphocytes was greater than 35%. Overall, 88 (72%) of 122 HIV-infected individuals without evidence of infectious or neoplastic lung disease had a lymphocytic alveolitis. These data suggest that the lungs may be involved early in the course of HIV infection and produce both symptomatic and asymptomatic processes.

Additional, albeit more inferential, information concerning idiopathic processes in HIV-infected persons was provided by Shaw and associates (63). These investigators found that the transfer factor for carbon monoxide was normal in HIV seropositive patients with no respiratory symptoms (this group included patients with lymphadenopathy) but that patients with symptomatic HIV infection apparently not involving the lungs (ARC, nonpulmonary Kaposi's sarcoma and other symptomatic processes) had abnormal values. As with the findings on BAL described by Gullion and coworkers, these observations suggest early asymptomatic lung involvement associated with HIV infection without identifiable secondary processes.

References

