All HIV seropositive subjects

Predictive variables

Absolute and relative numbers of CD4 cells. The CD4 cells will be grouped into 3 categories (>399, 200-399, <200) in some analyses.

Confounding variables

Antiviral therapy

Preventive therapy for HIV-related lung diseases

Outcome variables

Specific HIV-related lung diseases

Analysis

Regression models, appropriate when time dependant covariates are present, will be used to study this question.

Question 9. Do HIV infected persons who have not had lung diseases diagnosed have a greater incidence/prevalence of respiratory symptoms, pulmonary function abnormalities and unexplained radiographic findings than HIV seronegative subjects in the same transmission category?

Groups studied

All HIV seropositive and seronegative subjects

Predictive variables

HIV status

Transmission category

Confounding variables

Previous or current lung disease (recognized HIV-related or nonHIV- related)

Smoking

Outcome variables

Symptoms

Vital capacity, total lung capacity, forced expiratory volume in one second, diffusing capacity

Radiographic findings

Analysis

Analytic strategies involving regression models (linear and logistic) will be used

Question 10. Does pulmonary function deteriorate more rapidly in HIV infected persons who have not had lung diseases diagnosed compared with HIV seronegative subjects in the same transmission category?

Groups studied

All HIV seropositive and seronegative subjects

Predictive variables

HIV status

Transmission category

Confounding variables

Previous or current lung disease (recognized HIV-related or nonHIV-related)

Smoking

Outcome variables

Changes in vital capacity, total lung capacity, forced expiratory volume in one second, diffusing capacity over time

Analysis

Regression models will be used to address these questions.

Appropriate measures of decline (change) in lung function measurements will be used as outcome variables

Precision

Half-width 95% confidence intervals of DLCO for A versus C and B versus C are 2.0 for IV drug users and 1.3 for gays.

Question 11. How sensitive are symptoms for specific HIV-related lung diseases?

Groups studied

All HIV seropositive and seronegative subjects

Predictive variables

Fever (> 38R oral for > 5 days)

Cough (with or without sputum for > 5 days)

Shortness of breath (mild to moderate > 5 days, severe > 1 day)

Confounding variables

Preexisting lung disease

NonHIV-related lung diseases

Outcome variables

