Presence of specific HIV-related lung diseases (Appendix 2)

Absence of specific HIV-related lung diseases. Determined by lack of findings on evaluations as specified in Section 7.2.4 or by clinical course during one month following the evaluation

Analysis

Calculation of sensitivity. Regression models will be used to adjust for confounding variables.

Question 12. Does diagnosis of *P. carinii* pneumonia by intensive screening decrease both short- and long-term mortality?

Groups studied

All HIV seropositive subjects

Predictive variables

Diagnosis by intensive or routine screening or by symptom evaluation

Confounding variables

Treatment regimens for *P. carinii* pneumonia

Coexisting diseases

Antiviral therapy

Preventive therapy for HIV-related lung diseases

Outcome variables

Mortality rate at one month after diagnosis of *P. carinii* pneumonia

Median survival from time of study entry

Median survival from estimated time of HIV infection using slope of decline in CD4 cells

Analysis

Appropriate regression models and nonparametric techniques will be used to address this question

Precision

Half-width 95% confidence interval on long-term mortality rate differences between "routine" and "intensively" screened groups is 6%.

Question 13. Does diagnosis of P. carinii pneumonia by intensive screening decrease number of days of hospitalization?

Groups studied

All HIV seropositive subjects

Predictive variables

Diagnosis by intensive or routine screening or by symptom evaluation

Confounding variables

Treatment regimens for P. carinii pneumonia

Coexisting diseases

Antiviral therapy

Preventive therapy for HIV-related lung diseases

Outcome variables

Days in hospital after PCP diagnosis

Analysis

These data will be analyzed using linear models.

Question 14. Does diagnoses of P. carinii pneumonia by intensive screening decrease the rate of deterioration in performance status?

Groups studied

All HIV seropositive subjects

Predictive variables

Diagnosis by intensive or routine screening or by symptom evaluation

Confounding variables

Treatment regimens for P. carinii pneumonia

Coexisting diseases

Antiviral therapy

Preventive therapy for HIV-related lung diseases

Outcome variables

Rate of decline in performance score

Analysis

These data will be analyzed using linear models.

Appendix 11

Protocol Changes

1. New Date of Protocol
2. Page 40, #10: "... or other qualified professional staff".

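### At follow-up only symptoms or a scheduled film start the diagnostic evaluation, so Question 11's sensitivity of symptoms is open to verification bias and depends on the film schedule

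*Protocol*

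**What the plan says.** Section 7.2.4 gives two ways into the diagnostic evaluation. "The diagnostic evaluation may be triggered by the occurrence of symptoms", whether at or between visits, "or by chest radiograph detected on scheduled screening examinations". Pulmonary function is not named. Later in the same section, the second item under pulmonary function abnormalities resets a subject's DLCO baseline when a 20% drop led to an invasive work-up without a definite diagnosis.

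Appendix 1, Question 11 asks: "How sensitive are symptoms for specific HIV-related lung diseases". Presence of disease follows the Appendix 2 definitions. Absence is "Determined by lack of findings on evaluations as specified in Section 7.2.4", or by the clinical course in the month after the evaluation. The analysis entry reads: "Calculation of sensitivity. Regression models will be used to adjust for confounding variables".

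Secondary objective 4 (Section 2) is "To measure the frequency with which HIV-related lung diseases are present in HIV-infected persons who do not have symptoms".

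Table 6 sets films and pulmonary function tests every 3 months in subgroups A-2 and B-2 and every 12 months in A-1, B-1 and C. Induced sputum is scheduled at entry only.

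**The concern.** Sensitivity is the proportion of all disease that shows symptoms, so its denominator must include disease without symptoms. Here symptoms are one of two gates to being looked at. Symptom-free disease with a normal film is either never counted or counted later, once symptoms appear, as a symptomatic case. Regression on confounders works on the cases that were found and cannot restore cases nobody sought.

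The protocol's own background expects silent disease. Section 3.10 cites lymphocytic alveolitis "in 27 (59%) of 46 HIV-infected subjects who had no respiratory symptoms, normal chest films and no lung infections or neoplasia", and Section 4 cites reduced pulmonary function in patients without respiratory symptoms. At stake is a statement about how far symptoms can be relied on. That figure would also shift with how often films are taken, which the randomisation sets at two levels.

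**Working it through.** **Routes at follow-up for a symptom-free subject with a normal film**

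- Gallium scan: reserved for symptomatic subjects (7.2.4, item 5).
- Induced sputum: needs symptoms plus an abnormal film or scan (7.2.4, item 6) and is excluded from scheduled follow-up (7.2.3, Table 6).
- Diagnostic algorithms (7.2.7): every figure title concerns a radiographic abnormality. The figures themselves are not in the text at hand.
- Abnormal spirometry without symptoms: expressly not worked up (7.2.4).
- DLCO: the baseline clause is conditional on a work-up having happened and orders none. Appendix 8 mentions reduced DLCO only for serum at symptom-generated visits.
- Routine lavage in Appendix 5 is optional, without saying for whom.

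The change list in Appendix 11 records that pulmonary function was taken out of the trigger sentence. It is used here only to show that the present wording is not a text-extraction fault.

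**Direction and size**

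The protocol gives no figure for Question 11 or objective 4, so there is none to reproduce. Let S be true sensitivity, vS the probability that symptomatic disease is verified, and vA the same for symptom-free disease:

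observed = S·vS / [S·vS + (1 − S)·vA]

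Observed exceeds S when vS > vA, equals it when vS = vA, and falls below it when vS < vA.

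Assumption: half of disease is film-visible, with or without symptoms. The only figure in the documents is the 50% normal films reported for nonspecific interstitial pneumonitis in Section 3.10, from AIDS patients with pneumonitis. Then vA = 0.50 and vS = 0.50 + 0.50g, where g is the share of film-negative symptomatic disease that is verified. For S = 0.70:

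| g | vS | observed |
|---|---|---|
| 0 | 0.50 | 0.35/(0.35 + 0.15) = 0.70 |
| 0.5 | 0.75 | 0.525/(0.525 + 0.15) = 0.78 |
| 0.9 | 0.95 | 0.665/(0.665 + 0.15) = 0.82 |
| 1 | 1.00 | 0.70/(0.70 + 0.15) = 0.82 |

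Over the same range of g, a true 0.50 reads 0.50 to 0.67 and a true 0.90 reads 0.90 to 0.95. With S = 0.70 and vS = 0.95, taking vA as 0.25 gives 0.90 and as 0.75 gives 0.75. A low vA is plausible, because the silent phase must also coincide with a scheduled film.

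Reversal: if half of symptomatic disease is dropped from vS = 0.95, vS = 0.475 and observed = 0.3325/(0.3325 + 0.15) = 0.69.

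**Illustrations of mechanism only**

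- Section 3.10: "Overall, 88 (72%) of 122 HIV-infected individuals without evidence of infectious or neoplastic lung disease had a lymphocytic alveolitis". Of those 88, 27 (31%) were symptom-free with normal films and would not be reached. The denominator falls to 61, a factor of 88/61 = 1.44.
- Film schedule: assume a progressive disease with a silent phase of w weeks, film-visible in half of cases, and films every T weeks. The share of diagnosed disease with symptoms at diagnosis is 1 − 0.5·w/T. For w = 2, 4 and 8 this is 92%, 85% and 69% at T = 13, against 98%, 96% and 92% at T = 52. The phase lengths are assumed.

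**The case against.** **Other routes exist.** Section 7.2.8 brings in records from outside clinicians, and the autopsy procedures in Appendix 5 examine the lungs whatever the earlier symptoms or film. This stands: such cases can be diagnosed. But these routes are incidental, their uptake is not stated, and they do not verify living symptom-free subjects systematically. Sputum at a one-month visit that replaces a routine one (7.2.6) adds little, since those visits follow symptoms, an evaluation, treatment or an entry abnormality.

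**Objective 4.** A reader might infer that the whole objective counts only film-visible disease. The documents do not support that. Entrants have no new or worsening pulmonary symptoms (7.1.3, item 7). They have induced sputum at entry (Group B in 7.2.1; Groups A and B in Table 6). An initial DLCO below 75% is repeated at one month and evaluated if worse (7.2.6). These routes need no film finding.

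**Direction.** A reader might take upward bias as certain. It is not. Section 7.2.4 also stops evaluation for explained symptoms, fever alone with a normal film, presumed bronchitis, explanatory airways obstruction and a negative gallium scan. However, the fever-only and gallium exits apply to normal films, so with equal film shares they alone can only bring vS down to vA. Reversal needs film-positive symptomatic disease to go unverified too.

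**The illustrations.** The 1.44 should not be read as the size of the bias: alveolitis is not an Appendix 2 diagnosis, and the series excluded infection and neoplasia. The film-schedule model shows dependence on schedule only. If every case eventually had symptoms, sensitivity per episode would be 100% and all six readings would lie below it.

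**Scope.** Appendix 1 says its list of methods is not exhaustive, and Question 11 is not among the four questions given precision calculations in Appendix 3. Both are true. Reporting by schedule could sit in an analysis plan, but no analysis recovers disease that was not sought. Earlier, wider triggers may also have produced some diagnoses before this version, but how many is not stated.

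**Conclusion.** The point holds for follow-up. Under the current text the study's evaluation starts only from symptoms or a scheduled film, so Question 11 cannot deliver an unbiased sensitivity of symptoms. Since new or worsening pulmonary symptoms bar entry, Question 11 rests on follow-up data.

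The expected bias is upward, conditional on symptomatic disease being verified more often than symptom-free disease. With half of disease film-visible in both groups, and every film-visible silent case caught, a true 70% reads between 70% and 82%. All inputs except the 50% normal-film share are assumptions, and that share is borrowed from one disease in a different population. The fourfold difference in film frequency is a documented fact, so the reading can differ between arms for the same disease. How much it differs is not known.

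Objective 4 is affected only for incident disease. The primary objective is not challenged here, and no claim is made about Questions 10 or 12. The DLCO clause should not be read as a live trigger; it is inconsistent with the trigger sentence and needs aligning.

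**What to change.** 1. Restate Question 11 as the share of diagnosed disease that had symptoms at diagnosis, reported separately for the 3-monthly and 12-monthly film schedules.
2. Limit objective 4 during follow-up to film-detectable disease, and take the film-independent prevalence estimate from entry, where sputum and the DLCO rule apply.
3. Align the DLCO baseline clause in Section 7.2.4 with the trigger sentence, so that it no longer implies a work-up that nothing orders.

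All three are wording changes. The trigger rule, visits and procedures stay as they are. The cost is that the study no longer claims a true sensitivity of symptoms. Verifying a sample of symptom-free subjects by sputum or lavage is not recommended. It adds procedures and could not confirm lymphoid or nonspecific interstitial pneumonitis, which Appendix 2 defines by histology in lung tissue.
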